3.5. Protocol Deviations

Subjects with eligibility and major protocol deviations will be summarized and listed, as appropriate. Protocol deviations will be based on clinical review for the following aspects, but

not limited to: (1) eligibility, (2) treatment compliance, (3) patient safety, and (4) efficacy assessment deviation. Protocol deviations will be closely monitored during the execution of the study and the final set of protocol deviation criteria will be finalized before database lock.

3.6. Prior and Concomitant Medications

Prior and concomitant medications will be summarized by the World Health Organization Drug Dictionary (WHO-DD) therapeutic class, pharmacological class, and preferred term.

4. EFFICACY

The primary population for the primary efficacy endpoint, ORR, is the all-treated. Sensitivity analysis will be performed on the response-evaluable population, if deemed necessary. Unless otherwise specified efficacy analyses will be based on the all-treated population.

4.1. Analysis Specifications

4.1.1. Level of Significance

If deemed applicable, all tests will be 1-sided. The primary efficacy endpoint will be tested at the overall significance level of 0.025. For result presentation purpose, a 2-sided 95% confidence interval will be used.

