12.3. Sample Size Determination

This is a Phase 1/2a dose optimization and expansion study. For Part A, a statistical design based on the approach described in Ji, et al. (2010)³⁰ and Ji and Wang (2013)^{29,30} will be used. This method requires a definition of an equivalence interval (EI), $[0.25; 0.30]$, in which any dose is considered as a potential candidate for the true MTD, where 0.30 is the targeted DLT rate. Defining an EI results in the partition of the unit interval $(0, 1)$ into 3 subintervals; $(0; 0.25)$, $[0.25, 0.30]$, and $(0.30; 1)$. Doses in these 3 intervals are deemed lower, close to, and higher than the MTD, respectively. At least 6, and up to 9 subjects may be treated in each cohort in Part A. Approximately 18 subjects may be enrolled in Part A.

Part B, Cohorts B1 (CLL/SLL), B2 (FL), B3 (DLBCL), and B4 (Richter syndrome) are designed to evaluate the feasibility and safety of treating subjects with ibrutinib in combination with nivolumab and to evaluate preliminary activity. The sample size is calculated based on the following assumptions (denoting the true response rate of ibrutinib in combination with nivolumab as p):

- The overall response rate under null hypothesis is 20%
- The overall response rate under alternative hypothesis is at least 38%
- The probability to mistakenly rejecting the null hypothesis when it is actually true is 0.1 (one-sided).
- The probability to correctly rejecting null hypothesis when alternative hypothesis is true is at least 0.8

Under the above assumptions, the study will enroll approximately 35 subjects to get at least 32 response-evaluable subjects in each cohort of Part B (dose expansion; Cohorts B1, B2, B3, and B4).

Approximately 158 subjects (with up to 18 subjects in Part A and approximately 140 subjects in the Part B, dose expansion) will be enrolled in this study.

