1.4. Sample Size Justification

The sample size is calculated based on the following assumptions:

- The overall response rate under null hypothesis is 20%
- The overall response rate under alternative hypothesis is at least 38%
- The probability to mistakenly rejecting the null hypothesis when it is actually true is 0.1 (one-sided).
- The probability to correctly rejecting null hypothesis when alternative hypothesis is true is at least 0.8

Under the above assumptions, the study will enroll approximately 35 subjects to get at least 32 response evaluable subjects in each cohort of Part B (Cohorts B1, B2, B3, and B4).

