4.2.2. Analysis Methods

The response rate and its 95% exact (Clopper-Pearson) CI will be calculated. Subgroup analysis will be provided. Sensitivity analysis will be performed using the response-evaluable population.

A listing of tumor response by assessment visit will be provided.

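### The SAP tests ORR at one-sided 0.025, but the Part B cohorts were sized at one-sided 0.10; the planned test has about 60% power, not 80%

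*SAP*

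**What the plan says.** **Sizing.** SAP section 1.4 and Protocol section 12.3 give the same assumptions for each of cohorts B1 to B4: a response rate of 20% under the null and at least 38% under the alternative. On type I error the SAP states "The probability to mistakenly rejecting the null hypothesis when it is actually true is 0.1 (one-sided"), and on power the Protocol states "The probability to correctly rejecting null hypothesis when alternative hypothesis is true is at least 0.8". The result in SAP section 1.4 is that "the study will enroll approximately 35 subjects to get at least 32 response evaluable subjects in each cohort of Part B".

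**Analysis.** SAP section 4.1.1 begins "If deemed applicable, all tests will be 1-sided" and continues "The primary efficacy endpoint will be tested at the overall significance level of 0.025". It adds that a two-sided 95% interval is used to present results. SAP section 4.2.2, on the analysis of the primary endpoint, names no test and no success count; it says "The response rate and its 95% exact (Clopper-Pearson) CI will be calculated".

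**Population.** SAP section 4 makes the all-treated set primary for ORR, so n is about 35 per cohort. Protocol section 12.4 uses the response-evaluable set, at least 32 by design.

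**Hypotheses.** SAP section 1.3 sets the question of whether ORR exceeds 20% for each Part B cohort separately. No multiplicity rule is given.

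**The concern.** The endpoint and the sidedness are the same in both places, but the level used for testing is a quarter of the level used for sizing. A sample size supports a power statement only for the test it was derived for, so the 80% on which each Part B cohort was justified does not describe the test in SAP section 4.1.1.

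Two things are at stake. First, an active regimen has a much larger chance of missing the criterion than the reader is told. Second, there is a band of results that reject 20% under one section of the SAP and not under another, which leaves the choice of rule open after the data are seen.

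The word *overall* in section 4.1.1 adds a further doubt. With four separate cohort hypotheses it could mean 0.025 for each cohort or 0.025 shared among them.

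**Working it through.** **Inputs.** Null rate 0.20, alternative 0.38, sizing level 0.10 one-sided and n = 32 evaluable or 35 enrolled (SAP 1.4, Protocol 12.3); testing level 0.025 one-sided (SAP 4.1.1); exact Clopper-Pearson 95% interval (SAP 4.2.2).

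**Method.** Exact single-arm binomial. For each n and level α, take the smallest count c with P(X ≥ c | n, 0.20) ≤ α. Power is then P(X ≥ c | n, 0.38).

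**Step 1: reproduce the plan's figure at 0.10.** For n = 32, P(X ≥ 9 | 0.20) = 0.175 is too large and P(X ≥ 10 | 0.20) = 0.090 qualifies, so c = 10. Power is P(X ≥ 10 | 0.38) = 0.833. The smallest n reaching 80% by this method is 32, which matches the plan exactly. For n = 35, c = 11, actual level 0.075, power 0.835.

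**Step 2: apply the SAP's testing level.**

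| n | c at 0.10 | power | c at 0.025 | actual level | power |
|---|---|---|---|---|---|
| 32 | 10 | 83.3% | 12 | 0.0167 | 58.9% |
| 33 | 11 | 76.5% | 12 | 0.0216 | 64.0% |
| 34 | 11 | 80.3% | 13 | 0.0109 | 55.3% |
| 35 | 11 | 83.5% | 13 | 0.0142 | 60.4% |

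The movement between adjacent n is binomial discreteness. At the two design sizes power is 59% to 60%; over n = 32 to 35 it runs from 55% to 64%.

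**Step 3: check against the confidence interval.** The Clopper-Pearson 95% lower limits are 16.9% for 11/35, 19.1% for 12/35 and 21.5% for 13/35. Requiring the lower limit to exceed 20% therefore gives c = 13 at n = 35. At n = 32 the limit first exceeds 20% at 12 responders (21.1%). These are the 0.025 cutoffs.

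**Step 4: size of the zone where the two rules disagree, at a true rate of 38%.**
- n = 35, 11 or 12 responders: 0.835 − 0.604 = 0.231. The one-sided p-values are 0.075 and 0.034.
- n = 32, 10 or 11 responders: 0.833 − 0.589 = 0.244.

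**Step 5: what 80% power at 0.025 would take.** With n = 35 and c = 13, the true rate would have to be about 43%. With a true rate of 38%, n = 52 is the first size to reach 80% (82.4%), and power stays at or above 80% from n = 54.

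**Step 6: the other reading of *overall*.** This is an assumption; neither document states a split. An equal share among four cohorts is 0.025/4 = 0.00625. Then c = 13 at n = 32 (power 44.5%) and c = 14 at n = 35 (power 46.7%).

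**Sensitivity to method.** A normal approximation at 0.025 gives 68.5% (n = 32) and 71.9% (n = 35), or 61.8% and 65.7% with continuity correction. All are below 80%. The exact method is the proper comparison because it reproduces n = 32 and matches the SAP's exact interval.

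**The case against.** The strongest case against is that no decision rests on the test. Section 4.1.1 opens conditionally, SAP section 4.2.2 and Protocol section 12.4 ask only for a rate and its interval, the hypothesis is framed as evaluating and describing, and neither document contains a success rule. On that view the cutoffs above are derived by the reader, the estimate and interval are identical whichever level applies, and the stricter level cannot inflate false positives in a single-arm Phase 1/2a study.

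Part of this stands. The success and failure labels apply only if a test is made or the interval is compared with 20%. The sizing arithmetic itself is correct at 0.10; the fault is that two levels are in force. The 59% to 60% belongs to n = 32 and n = 35, not to every n between. The figure of 35 is also an assumption for the primary analysis: SAP sections 1.1 and 2.1 allow summaries by disease type pooled over Parts A and B, where n would differ.

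The conflict remains. The sentence setting 0.025 is itself unconditional. If no test is intended, it should not be there, and leaving its applicability to later judgement is not prespecification. The natural informal reading, whether the 95% interval excludes 20%, lands on the stricter cutoff anyway. A stricter level is conservative for false positives only: it raises the chance of missing a 38% response rate from about 17% to about 40%, and the plan does not say so.

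**Conclusion.** The concern holds. The current SAP contradicts itself, and contradicts the Protocol, on the level for the primary endpoint, and nothing in either document reconciles them. Power of at least 80% is right at one-sided 0.10 (83.3% at n = 32, 83.5% at n = 35). For the test written in SAP section 4.1.1 it is 58.9% and 60.4%, and no n from 32 to 35 exceeds 64.0%. At a true rate of 38% the two rules disagree in roughly one cohort in four. This rests on exact binomial calculation, each Part B cohort analysed separately at its design size, and 0.025 applying to each cohort. If 0.025 were shared equally over four cohorts, power would be about 45% to 47%. The inconsistency must be resolved, because it concerns the criterion for the primary endpoint.

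**What to change.** Use one level throughout, by either route.

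- **(a) Align the test with the sizing.** Set SAP section 4.1.1 to one-sided 0.10 per cohort, state the success count (10 or more of 32 evaluable, or 11 or more of 35 all-treated, with the rule for other n), and label the 95% interval as descriptive. The two-sided interval that matches this level is 80%.
- **(b) Keep 0.025.** State in SAP section 1.4 that the test has about 60% power against 38% (13 or more of 35; 12 or more of 32 gives 59%). Protocol section 12.3 is consistent in itself, but it should carry the same statement or a cross-reference so that the two documents agree.

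In both cases delete *overall*, or say that each cohort is tested separately without multiplicity control. If the latter, it helps to give the consequence: for four independent cohorts at their nominal levels, the chance of at least one false rejection is 1 − 0.90⁴ = 34.4% under (a) and 1 − 0.975⁴ = 9.6% under (b). If no test is intended, section 4.1.1 should say that instead.

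The cost is a wording change and, under (b), a less favourable stated power. No patients are added.

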4.1.2. Data Handling Rules

Unless otherwise specified, missing values will not be imputed.

4.1.3. General Analysis Considerations

For this study and its CSR, analyses of disease response and disease progression are based on investigator assessments. These assessments are based on IWCLL [International Workshop on Chronic Lymphocytic Leukemia (Hallek 2008)] for CLL patients and the Lugano Classification by Cheson (2014) for SLL, FL, DLBCL and Richter syndrome and using data collected at the clinical cutoff. Detailed criteria for response category can be found in Section 10.1 of the protocol. All the additional data collected after the clinical cutoff will be summarized in the CSR addendum.

4.2. Primary Efficacy Endpoint(s)

4.2.1. Definition

The primary endpoint is ORR, defined as the proportion of subjects who achieve partial response or better [PR(+L) or better], as assessed by the investigators at or prior to initiation of subsequent anti-cancer therapy. The primary efficacy analysis of ORR will be conducted at performed 6 months after the last subject has received the first dose of study medication, or earlier if that subject discontinues study therapy. The analysis will be based on the all-treated population.

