The efficacy endpoints are defined as follows, based on the IWCLL or the Lugano Classification by Cheson (2014), as appropriate for the disease:

- Overall response rate (ORR), which is defined as the proportion of evaluable subjects who achieve CR or PR, as assessed by the investigators.
- Duration of response (DOR) will be calculated from the date of initial documentation of a response (CR or PR) to the date of first documented evidence of progressive disease (or relapse for subjects who experience CR during the study) or death. Subjects who are progression-free and alive or have unknown status will be censored at the last tumor assessment.
- Progression-free survival (PFS) is defined as the duration from the date of first dose of study drug until the date of first documented evidence of progressive disease (or relapse for subjects who experience CR during the study) or death, whichever comes first. Subjects who are progression-free and alive or have unknown status will be censored at the last tumor assessment.
- Overall survival (OS) is measured from the date of first dose of study drug to the date of the subject's death. If the subject is alive or the vital status is unknown, the subject will be censored at the date the subject was last known to be alive.

PHARMACOKINETIC EVALUATIONS

Blood samples will be collected from all subjects for determination of plasma concentrations of ibrutinib and the PCI-45227 metabolite (if possible and judged relevant), as well as serum concentrations of nivolumab. Pharmacokinetic assessments will not be conducted post clinical cutoff.

IMMUNOGENICITY EVALUATIONS

Subjects will be monitored for anti-nivolumab antibodies throughout the study. Blood for serum anti-nivolumab antibody testing should be collected.

BIOMARKER EVALUATIONS

Biomarkers will be assessed in all subjects to further characterize the pharmacodynamic profile and to investigate the molecular efficacy of the ibrutinib and nivolumab combination regimen.

Biomarkers will be analyzed in:

- Tumor tissue
- Blood samples (collected serially)
- Fine-needle aspirates (from affected lymph nodes)
- Bone marrow aspirates or biopsies

After clinical cutoff, some biomarker assessments (bone marrow aspirate/biopsy) will no longer be conducted.

SAFETY EVALUATIONS

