- Overall response rate (CR or PR) will be calculated with 95% CI for each disease-specific cohort (B1, B2, B3, and B4) on the response-evaluable population.
- Progression-free survival and overall survival at 1 year will be evaluated using Kaplan-Meier method.
- Duration of response and duration of stable disease will be evaluated if there are sufficient data for responders within each cohort.

Table 1: Time and Events Schedule

| | Notes | Screening Period | Treatment Period (14 day cycles) | | | Follow-up Period ^a |
|---|--|---|---|--------------------------|-----|-------------------------------|
| | | up to 28 days before start of any study treatment | BASELINE ASSESSMENT CID1 (without run-in phase) CID-7 (with run-in phase) | Day 1, subsequent cycles | EOT | Q3m |
| 
Treatment Period begins with the first administration of study therapy. EOT visit is required for all subjects and should take place within 30 days after last dose of study therapy with a window of ± 7 days. If the subject requires subsequent anti-lymphoma/neoplastic therapy in the interim period between last dose of study drug and the EOT visit, then this visit should be completed just prior to initiation of subsequent therapy. Follow-up visits in all subjects will be completed every 3 months with a window of ± 7 days until death or end of study. Note that the first FU visit should be approximately 100 days after end of nivolumab therapy; during this first FU visit, additional sampling will be done.
 
After the clinical cutoff, subjects who are ongoing on treatment continue all assessment per protocol, however data collected on eCRF will be limited to at least: SAEs and AEs Grade ≥ 3, laboratory assessments (Grade ≥ 3 or clinically significant), efficacy assessments, survival status, and study treatment administration.
 
Per Amendment 7, subjects who are receiving study treatment will continue all assessments per protocol. Data collected in the eCRF will be further limited to: SAEs and Grade ≥ 3 AEs that are at least possibly related to treatment, AEs leading to discontinuation or modification, efficacy assessments, and study treatment administration.
 | | | | | | |
| Screening/Administrative | | | | | | |
| Informed consent | ICF must be signed before any study-related procedures are performed. | X | | | | |
| Eligibility criteria | | X | | | | |
| Demography/ Medical History | | X | | | | |
| Study Drug Administration | | | | | | |

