2. OBJECTIVES AND HYPOTHESIS

2.1. Objectives

Primary Objective

Part A (Dose Optimization Cohorts): The primary objective of Part A is to determine whether ibrutinib and nivolumab can be safely combined and to establish the recommended Phase 2 dose (RP2D) for this combination in subjects with hematological disorders.

Part B (Expansion Cohorts): The primary objective of Part B is to determine the preliminary activity of the ibrutinib/nivolumab combination regimen in subjects with relapsed/refractory CLL/SLL and poor prognosis (deletion 17p or deletion 11q), relapsed/refractory FL, relapsed/refractory DLBCL, or Richter syndrome in comparison to historical results.

Secondary Objectives

The secondary objectives are:

- To evaluate the safety profile of the ibrutinib and nivolumab combination regimen
- To assess overall response rate (ORR), duration of response, duration of stable disease, progression-free survival rate at 1 year, and overall survival at 1 year of the ibrutinib and nivolumab combination regimen
- To characterize and explore the pharmacokinetic profile of ibrutinib and nivolumab compared with existing single-agent treatment data; and the potential relationships between ibrutinib and nivolumab metrics of exposure with relevant clinical or biomarker information (Part A and B)

Exploratory Objectives

- To characterize the molecular effects of the ibrutinib and nivolumab combination regimen on tumor cells and the immune response; and identify biomarkers of response or resistance to the combination
- To evaluate the immunogenicity of nivolumab

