- Overall response rate, which is defined as the proportion of evaluable subjects who achieve CR or PR, as assessed by the investigators,
- Duration of response will be calculated from the date of initial documentation of a response (CR, or PR) to the date of first documented evidence of progressive disease (or relapse for subjects who experience CR during the study) or death. Subjects who are progression-free and alive or have unknown status will be censored at the last tumor assessment.
- Progression-free survival is defined as the duration from the date of first dose of study drug until the date of first documented evidence of progressive disease (or relapse for subjects who experience CR during the study) or death, whichever comes first. Subjects who are progression-free and alive or have unknown status will be censored at the last tumor assessment.
- Overall survival is measured from the date of first dose of study drug to the date of the subject's death. If the subject is alive or the vital status is unknown, the subject will be censored at the date the subject was last known to be alive.

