12.4. Efficacy Analyses

Part A: Individual best tumor responses and duration of response (defined as the time from first response to progression) will be listed for each dose cohort.

Part B: The following efficacy analyses will be performed to explore the clinical activity of ibrutinib in combination with nivolumab in each cohort in the treated population unless otherwise stated:

- Overall response rate (CR or PR) will be calculated with 95% CI for each disease-specific cohort B1, B2, B3, and B4 on the response-evaluable population.
- Progression-free survival and overall survival at 1 year will be evaluated using Kaplan-Meier method.
- Duration of response and duration of stable disease will be evaluated if there are sufficient data for responders within each cohort.

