Attachment 6.1: International Workshop on Chronic Lymphocytic Leukemia (IWCLL)

The International Workshop on Chronic Lymphocytic Leukemia (IWCLL) recommendations for the management of CLL in clinical studies and general practice are presented below (Hallek 2008)²³.

| Response Category | Definition |
|---------------------------------|--|
| Complete Response (CR) | 
Group A^{1,2}
 
 • Lymphadenopathy^a: none >1.5cm • Hepatomegaly: none • Splenomegaly: none • Blood lymphocytes: <4000/μL • Marrow^c: Normocellular, <30% lymphocytes, no B-lymphoid nodules. Hypocellular marrow defines CRi 
Group B^{1,2}
 
 • Platelet count: >100,000/μL • Hemoglobin>11 g/dL • Neutrophils^c: >1500/μL 
Complete Response with an Incomplete Marrow Recovery (CRi) is defined as a complete response with an incomplete recovery of the subject's bone marrow. Subjects who have a CRi fulfill the criteria for a CR, but continue to have persistent anemia, thrombocytopenia, or neutropenia, and a hypocellular bone marrow. These cytopenias are due to drug toxicity in the bone marrow and are not due to any evidence of CLL.
 |
| Partial Response (PR) | 
Group A^{1,3}
 
 • Lymphadenopathy^a: Decrease \geq50% • Hepatomegaly: Decrease \geq50% • Splenomegaly: Decrease \geq50% • Blood lymphocytes: Decrease \geq50% from baseline • Marrow^c: 50% reduction in marrow infiltrates or B lymphoid nodules 
Group B^{1,3}
 
 • Platelet count: >100,000/μL or increase \geq50% over baseline • Hemoglobin: >11g/dL or increase \geq50% over baseline • Neutrophils^c: >1500/μL or increase \geq50% over baseline 
Nodular Partial Response (nPR) nPR is a response where subjects meet the criteria for a CR, but the bone marrow biopsy shows that there are still B-lymphoid nodules present. These nodules are residual disease and therefore the subject is termed an nPR.
 
Partial Response (PR) with Lymphocytosis PR with lymphocytosis is a response where subjects meet the criteria for a PR and have persistent lymphocytosis.
 |
| Stable Disease (SD) | Not meeting criteria for CR, CRi, nPR, PR, or PD |
| Progressive Disease (PD) | 
Group A^{1,4}
 
 • Lymphadenopathy^a: increase \geq50% or appearance of new lesions >1.5 cm |

| Response Category | Definition |
|-------------------|--|

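### In CLL the SAP counts PR with lymphocytosis as a response, the protocol counts CR or PR, Attachment 6.1 can be read either way, and the protocol's CR/PR rate is never produced

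*SAP*

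**What the plan says.** **Protocol.** The synopsis and Section 10.1 give the same definition: "Overall response rate, which is defined as the proportion of evaluable subjects who achieve CR or PR, as assessed by the investigators". Section 12.4 then plans the analysis: "Overall response rate (CR or PR) will be calculated with 95% CI for each disease-specific cohort", on the response-evaluable population. Duration of response (DOR) in Section 10.1 also runs from the first CR or PR.

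**SAP.** Section 4.2.1 defines the primary endpoint as "defined as the proportion of subjects who achieve partial response or better [PR(+L) or better" in the all-treated population. Sections 1.1, 2.4.1, 4.3.1 and 7.5 use the same PR(+L) threshold. Section 2.7 gives PRL its own best-response rank (5, below PR at 3 and nodular PR at 4) and counts time to response in CLL from the onset of PRL. The sensitivity analysis in Section 4.2.2 changes the population only, and Section 1.1 keeps PR(+L) for that population too.

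**Response criteria.** SAP 4.1.3 sends the reader to Protocol 10.1 for the categories, and Protocol 10.1 leads to Attachment 6.1 for CLL. The PR row there says: "PR with lymphocytosis is a response where subjects meet the criteria for a PR and have persistent lymphocytosis". The SD row reads: "Not meeting criteria for CR, CRi, nPR, PR, or PD". Footnote 3 adds that any PR needs a lymphocyte count that is back to normal or down by more than half, if it was raised at baseline.

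**The concern.** The primary endpoint should classify a given CLL subject the same way in both documents. Here a subject whose best response is PR-L is a responder under the SAP and may or may not be one under the protocol.

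Three results depend on the answer: the CLL ORR, the date from which DOR is counted, and the set of subjects who enter the DOR analysis.

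The comparison with outside data depends on it as well. The Part B primary objective covers CLL/SLL, FL, DLBCL "or Richter syndrome in comparison to historical results". Protocol 1.2.4 reports ibrutinib-alone rates in CLL/SLL both with and without PR-L, and neither document says the definitions must match when the comparison is made.

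**Working it through.** **1. The plan's own figure.** Inputs (Protocol 12.3, SAP 1.4): null 20%, alternative 38%, one-sided alpha 0.1, power at least 0.8, 32 evaluable subjects per cohort. With an exact binomial test at n = 32, success at 10 or more responders gives P(X ≥ 10 | 0.20) = 0.0898 and P(X ≥ 10 | 0.38) = 0.833. At n = 31 the power is 0.799. So 32 reproduces. The 20% and 38% are the same in both documents, although the responder definitions are worded differently.

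**2. Is PR-L a PR?**
- For: the PR row places PR-L inside the PR category and says such subjects satisfy the PR criteria. The SD row does not mention PR-L, which fits if it is already a PR.
- Against: footnote 3 may exclude PR-L subjects whose count was raised at baseline and has neither normalized nor halved. The SD row names CRi and nPR beside CR and PR, so its silence on PR-L is not decisive.
- Usage elsewhere: SAP 2.7 ranks PRL apart from PR, and Protocol 1.2.4 prints ORR with and without PR-L as different numbers. Both treat PR-L as distinct.

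**3. Is the protocol's rate recoverable from the SAP?** The primary and sensitivity analyses both use PR(+L). SAP 4.2.2 also plans a by-visit response listing, from which CR/PR could be counted by hand, but no CR/PR rate with CI is planned.

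**4. Possible size.** Protocol 1.2.4 has two pairs for previously treated CLL/SLL on ibrutinib alone, both assessed by an independent review committee (IRC). The treatment-naive pair is left out because B1 requires relapsed or refractory disease.

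| Source | Without PR-L | With PR-L | Difference | PR-L-only share of responders |
|---|---|---|---|---|
| Phase 2 and extension | 76.2% | 79.2% | 3.0 points | 3.0/79.2 = 3.8% |
| Phase 3 | 42.6% | 62.6% | 20.0 points | 20.0/62.6 = 31.9% |

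To illustrate, assume all 35 B1 subjects have CLL (the CLL/SLL split is not given), take responders = rate × 35, rounded, and use Clopper-Pearson intervals:
- First pair: 27/35 = 77.1% (59.9 to 89.6) against 28/35 = 80.0% (63.1 to 91.6).
- Second pair: 15/35 = 42.9% (26.3 to 60.6) against 22/35 = 62.9% (44.9 to 78.5).

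**5. Effect on the 20% reference.** Take the lowest of these rates, 42.6% without PR-L. Under the design rule, P(X ≥ 10 | n = 32, 0.426) = 0.93. If instead the 95% exact lower limit must exceed 20%, the first qualifying count at n = 35 is 13 (lower limit 21.5%), and P(X ≥ 13 | n = 35, 0.426) = 0.79. At 76.2%, P(X ≥ 10 | n = 32) is essentially 1.

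**The case against.** The strongest reply is that nothing differs. The PR row says PR-L subjects meet the PR criteria, and footnote 3 need not conflict: a count can fall by more than half from a high baseline and still be raised. On that reading PR-L is a kind of PR, CR or PR already includes it, and the SAP only spells this out, as Protocol 12 allows when it leaves specific details to the SAP. This reading is tenable and cannot be ruled out from the documents. Attachment 6 also calls itself a summary of published criteria, so an inference from what one row omits is weak. What the reply does not explain is why SAP 2.7 ranks PRL below PR, or why Protocol 1.2.4 gives two different rates.

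A reader might go further and infer that the SAP definition would manufacture an apparent nivolumab effect. Suppose the combination is no better than ibrutinib alone, and success means that the 95% exact lower limit at n = 35 exceeds the historical CR/PR rate. For the 42.6/62.6 pair this needs 22/35, with probability 0.56 if PR(+L) is counted and 0.013 on the matched definition. For the 76.2/79.2 pair it needs 32/35, with probabilities 0.048 and 0.020. The documents do not support that inference. They set no such rule, they frame the objective as descriptive, Protocol 1.2.4 prints both definitions side by side, B1 admits SLL, and the historical rates are IRC-assessed while this trial uses investigator assessment. The figures show only how much a mismatch could matter.

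**Conclusion.** The point holds as a gap in definition and reporting for IWCLL-assessed CLL. The documents word the responder definition differently, Attachment 6.1 does not clearly settle the status of PR-L, and the rate Protocol 12.4 plans is not among the SAP analyses. It covers CLL subjects in B1, and Part A CLL subjects wherever SAP 1.1 applies PR(+L): cohorts A1 and A2 and the disease-type summaries. Subjects with SLL, FL, DLBCL or Richter syndrome are assessed by Lugano criteria, which have no PR-L category.

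The size in this trial is unknown. It is zero if PR-L is a subset of PR. Otherwise 3.0 to 20.0 points is a guide, assuming the earlier IRC-assessed ibrutinib data carry over.

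A reader might infer that the test against 20% is at risk. It is not seriously so, since the quoted ibrutinib-alone rates clear 20% without PR-L. What could change is the ORR estimate, the DOR start date and the comparison with historical results. This should be fixed; confidence is medium because the effect depends on how Attachment 6.1 is read.

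**What to change.** 1. In Protocol Attachment 6.1, reconcile the PR row, the SD row and footnote 3 so that PR-L has one definition and one place. Align Protocol 10.1 and 12.4 with SAP 1.1, 2.4.1, 2.7, 4.2.1, 4.3.1 and 7.5 on whether PR-L counts as a response.
2. In SAP 4.2.2 and 4.3.1, report CLL ORR with exact 95% CI, and DOR, both with and without PR-L. Show PR-L as its own best-response category, which the ranking in SAP 2.7 already allows.
3. Compare each rate only with a historical rate on the same definition.

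The Amendment 7 rationale says the primary and secondary objectives have already been analyzed and published, so fixing the definition in advance may no longer be possible. Reporting both versions still is, in the CSR or in the CSR addendum that Protocol 3.1 and SAP 4.1.3 provide for.

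The cost is wording in two documents and one extra table from data already collected. The CR/PR rate shown may be lower than the PR(+L) rate, and its DOR may start later.
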